8.5.2. Independent Data Monitoring Committee (IDMC)

An IDMC will be assigned by the Sponsor prior to the beginning of the study and will provide ongoing oversight of the study.

The IDMC will provide study oversight throughout the duration of the study period (Day 1 through EOS). The IDMC will perform a review of safety data of all participants in Part 1. Enrollment and dosing in Part 2 will only commence following the IDMC's recommendation to proceed. A summary of safety and immunogenicity data with the intended dose for Part 2 will also be submitted to FDA for review and concurrence prior to initiation of enrollment in Part 2.

In Part 2, unblinded data will be provided to the IDMC to ensure halting rules are applied based on observations of events in the vaccine treatment groups, regardless of dose level.

Additionally, *ad hoc* meetings will be convened if any predefined halting rules (see Section 6.1) are met, any serious vaccine related events or trends are observed, or the IDMC has concerns of potential vaccine enhanced disease (following the occurrence of a COVID-19, as defined in Section 7.1.1).

Further details regarding data safety monitoring guidelines will be included in the IDMC Charter, which is the governing document that supersedes this section of the protocol.

_

Vaxart, Inc.

9. SUPPORTING DOCUMENTATION AND OPERATIONAL CONSIDERATIONS

9.1. Appendix 1: Regulatory, Ethical, and Study Oversight Considerations

9.1.1. Regulatory and Ethical Considerations

- This study will be conducted in accordance with the protocol and with the following:
 - Consensus ethical principles derived from international guidelines including the Declaration of Helsinki and Council for International Organizations of Medical Sciences (CIOMS) International Ethical Guidelines
 - Applicable ICH Good Clinical Practice (GCP) Guidelines
 - Applicable laws and regulations
- The protocol, protocol amendments, ICF, Investigator Brochure, and other relevant documents (e.g., advertisements) must be submitted to an IRB/IEC by the investigator and reviewed and approved by the IRB/IEC before the study is initiated.
- Any amendments to the protocol will require IRB/IEC approval before implementation of changes made to the study design, except for changes necessary to eliminate an immediate hazard to study participants.
- Protocols and any substantial amendments to the protocol will require health authority approval prior to initiation except for changes necessary to eliminate an immediate hazard to study participants.
- The investigator will be responsible for the following:
 - Providing written summaries of the status of the study to the IRB/IEC annually or more frequently in accordance with the requirements, policies, and procedures established by the IRB/IEC
 - Notifying the IRB/IEC of SAEs or other significant safety findings as required by IRB/IEC procedures
 - Providing oversight of the conduct of the study at the site and adherence to requirements of 21 CFR, ICH guidelines, the IRB/IEC, European regulation 536/2014 for clinical studies (if applicable), European Medical Device Regulation 2017/745 for clinical device research (if applicable), and all other applicable local regulations

9.1.2. Financial Disclosure

Investigators and sub-investigators will provide the sponsor with sufficient, accurate financial information as requested to allow the sponsor to submit complete and accurate financial certification or disclosure statements to the appropriate regulatory authorities. Investigators are responsible for providing information on financial interests during the course of the study and for 1 year after completion of the study.

9.1.3. Informed Consent Process

- The investigator or his/her representative will explain the nature of the study to the participant and answer all questions regarding the study.
- Participants must be informed that their participation is voluntary. Participants will be required to sign a statement of informed consent that meets the requirements of 21 CFR 50, local regulations, ICH guidelines, Health Insurance Portability and Accountability Act (HIPAA) requirements, where applicable, and the IRB/IEC or study center.
- The medical record must include a statement that written informed consent was obtained before the participant was enrolled in the study and the date the written consent was obtained. The authorized person obtaining the informed consent must also sign the ICF.
- Participants must be re-consented to the most current version of the ICF(s) during their participation in the study.
- A copy of the ICF(s) must be provided to the participant.

A participant who is rescreened is not required to sign another ICF if the rescreening occurs within 30 days from the previous ICF signature date.

9.1.4. Exclusion of Women, Minorities, and Children (Special Populations)

This clinical study will include women and men who are 18 years of age and older and volunteers of all races and ethnicities who meet the inclusion/exclusion criteria, regardless of religion, sex, or ethnic background.

9.1.5. Data Protection

- Participants will be assigned a unique identifier by the sponsor. Any participant records or datasets that are transferred to the sponsor will contain the identifier only; participant names or any information which would make the participant identifiable will not be transferred.
- The participant must be informed that his/her personal study-related data will be used by the sponsor in accordance with local data protection law. The level of disclosure must also be explained to the participant who will be required to give consent for their data to be used as described in the informed consent
- The participant must be informed that his/her medical records may be examined by Clinical Quality Assurance auditors or other authorized personnel appointed by the sponsor, by appropriate IRB/IEC members, and by inspectors from regulatory authorities.

9.1.6. Dissemination of Clinical Study Data

A clinical study report will be developed by the Sponsor at completion of data analysis. This report will be an integrated clinical and statistical report prepared according to the ICH E3 guidelines.

Sponsor will register the study and post study results regardless of outcome on a publicly accessible website in accordance with the applicable laws and regulations.

9.1.7. Data Quality Assurance

All participant data relating to the study will be recorded on printed or eCRFs unless transmitted to the Sponsor or designee electronically (e.g., laboratory data). The Investigator is responsible for verifying that data entries are accurate and correct by physically or electronically signing the eCRF.

The Investigator must maintain attributable, legible, contemporaneous, original, accurate, and complete documentation (source data) that supports the information entered in the eCRF.

The Investigator must permit study-related monitoring, audits, IRB/IEC review, and regulatory agency inspections and provide direct access to source data documents.

Details describing monitoring strategy (e.g., risk-based initiatives in operations and quality such as risk management and mitigation strategies and analytical risk-based monitoring), methods, responsibilities and requirements, including handling of noncompliance issues and monitoring techniques (central, remote, or on-site monitoring) are provided in the Monitoring Plan.

The Sponsor or designee is responsible for the data management of this study including quality review of the data.

The Sponsor maintains ultimate responsibility for the quality and integrity of study data, even if study-related duties and functions are transferred to other individuals or organizations (e.g., contractors or contract research organizations).

Study monitors will perform ongoing source data verification to confirm that data entered into the Case Report Form (CRF) by authorized site personnel are attributable, legible, contemporaneous, original, accurate, and complete from source documents; that the safety and rights of participants are being protected; and that the study is being conducted in accordance with the currently approved protocol and any other study agreements, ICH GCP, and applicable regulatory requirements.

Records and documents, including signed ICFs, pertaining to the conduct of this study must be retained by the Investigator per ICH-GCP and local regulations or institutional policies. No records may be destroyed during the retention period without the written approval of the Sponsor. No records may be transferred to another location or party without written notification to the Sponsor.

9.1.8. Source Documents

Source documents provide evidence for the existence of the participant and substantiate the integrity of the data collected. Source documents should be generated utilizing good documentation practices and are filed at the Investigator's site.

Source documents are original documents, data, and records from which the participant's CRF data are obtained. These include but are not limited to hospital records, clinical and office charts, laboratory and pharmacy records, diaries, microfiches, radiographs, and correspondence.

Data entered in the eCRF that are transcribed from source documents must be consistent with the source documents or the discrepancies must be explained. The Investigator may need to request

previous medical records or transfer records, depending on the study. Also, current medical records must be available.

The investigator must maintain accurate documentation (source data) that supports the information entered in the eCRF.

Study monitors will perform ongoing source data verification to confirm that data entered into the eCRF by authorized site personnel are accurate, complete, and verifiable from source documents; that the safety and rights of participants are being protected; and that the study is being conducted in accordance with the currently approved protocol and any other study agreements, ICH GCP, and all applicable regulatory requirements.

9.1.9. Publication Policy

The Sponsor will comply with the requirements for publication of study results. In accordance with standard editorial and ethical practice, the Sponsor will generally support publication of multicenter studies only in their entirety and not as individual site data. In this case, a coordinating investigator will be designated by mutual agreement. Requests for publication of site specific data should be presented to the Sponsor for review and approval at least 90 days prior to submission for publication.

9.2. Appendix 2: Safety Clinical Laboratory Tests

- The tests detailed in Table 8 will be performed by either the central testing laboratory or the local laboratory, unless otherwise specified.
- All safety laboratories, hematology and serum chemistry are to be drawn by standard phlebotomy techniques, into the central lab provided tubes or the site prescribed appropriate tubes for the specific tests and amounts prescribed by local laboratory. Refer to the laboratory manual for further details on specimen collection and handling procedures.
- Protocol-specific requirements for inclusion or exclusion of participant are detailed in Section 3.3 for Part 1 and Section 4.3 for Part 2 of the protocol.
- Additional tests may be performed at any time during the study as determined necessary by the investigator or required by local regulations.
- Investigators must document their review of each laboratory safety report.

 Table 8
 Protocol-Required Safety Laboratory Assessments

Test*	Testing Panel/Analytes
Hematology	Hemoglobin, hematocrit, platelet count ¹ , and complete white blood cell count
Serum Chemistry	Alanine aminotransferase (ALT), aspartate aminotransferase (AST), total bilirubin, BUN, creatinine, random glucose, potassium and sodium
Coagulation Tests	Tests for clotting parameters: PT/INR, aPTT and fibrinogen (performed as part of the safety laboratory testing at Screening)
Urinalysis	Protein, glucose ketones and hemoglobin
Other laboratory assessments	Hepatitis B surface antigen, hepatitis C virus antibody, and human immunodeficiency virus antibody types 1 and 2 (Screening only)
Urine drug screen	Amphetamines, methamphetamines, barbiturates, benzodiazepines, cocaine, opiates, methylenedioxymethamphetamine, phencyclidine, tetrahydrocannabinol
Other laboratory assessments	Female participants: Serum (screening) or urine pregnancy test, (human chorionic gonadotropin)

*Refer to the Schedule of Activities for Part 1 (Table 3) and Part 2 (Table 4) to determine which safety laboratory assessments are required for each study phase and specific site visits.

² If platelets are abnormal, a normal NaCitrate platelet test is needed

9.3. Appendix 3: Adverse Events: Definitions and Procedures for Recording, Evaluating, Follow-up, and Reporting

9.3.1. Definition of TEAE (Unsolicited and Solicited)

TEAE Definition

- A TEAE is any untoward medical occurrence in a clinical study participant, temporally associated with the use of study intervention, whether or not considered related to the study intervention, occurring after first dose of study drug.
- NOTE: A TEAE can therefore be any unfavorable and unintended sign (including an abnormal laboratory finding), symptom, or disease (new or exacerbated) temporally associated with the use of study intervention.

Definition of Unsolicited and Solicited TEAE

- Unsolicited TEAEs are any TEAEs reported spontaneously by the participant, observed by the study personnel during study visits or those identified during review of medical records or source documents. Unsolicited TEAEs (all TEAEs not collected in the Solicited Symptom Diary during the first week following each vaccination) will be monitored and collected from the time of each vaccination through 4 weeks post each vaccination (1st vaccination through Week 4 and 2nd vaccination through Week 8).
- Solicited TEAEs are predefined systemic signs and symptoms of reactogenicity for which the participant is specifically questioned, and which are noted by the participant in their Solicited Symptom Diary, including:
 - fever (any temperature 100°F or higher)
 - headache
 - myalgia (muscle pain)
 - abdominal pain
 - anorexia (defined and not eating)
 - nausea
 - vomiting
 - diarrhea
 - malaise/fatigue

Participants will utilize a Solicited Symptom Diary issued on the day of each vaccination to record solicited TEAE daily for the 1 week following each vaccination on Day 1 and Week 4.

9.3.2. Definition of MAAE

Medically Attended Adverse Events Definition

MAAEs are defined as TEAEs with medically-attended visits including hospital, emergency room, urgent care clinic, or other visits to or from medical personnel for any reason. Routine study visits will not be considered medically-attended visits. New onset of chronic illness/diseases (NOCI) and AEs of Special Interest (AESIs) will be collected as part of the MAAEs. MAAEs are to be reported for all participants from the moment of vaccination until 12 months after the vaccination. Refer to Appendix 5 (Section 9.5) for list of AESIs that should be monitored in this study.

Events Meeting the TEAE Definition

- Any abnormal laboratory test results (hematology, clinical chemistry, or urinalysis) or other safety assessments (e.g., vital signs measurements), including those that worsen from baseline, considered clinically significant in the medical and scientific judgment of the investigator.
- Exacerbation of a chronic or intermittent pre-existing condition including either an increase in frequency and/or intensity of the condition.
- New conditions detected or diagnosed after study drug administration even though it may have been present before the start of the study.
- Signs, symptoms, or the clinical sequelae of a suspected intervention- intervention interaction.
- Signs, symptoms, or the clinical sequelae of a suspected overdose of either study intervention or a concomitant medication. Overdose per se will not be reported as an AE/SAE unless it is an intentional overdose taken with possible suicidal/self-harming intent. Such overdoses should be reported regardless of sequelae.
- The signs, symptoms, and/or clinical sequelae resulting from lack of efficacy will be reported as TEAE or SAE if they fulfill the definition of TEAE or SAE. "Lack of efficacy" or "failure of expected pharmacological action" also constitutes an TEAE or SAE.

Events NOT Meeting the TEAE Definition

- Events that occurred from consent to pretreatment
- Medical or surgical procedure (e.g., endoscopy, appendectomy): the condition that leads to the procedure is the AE.
- Situations in which an untoward medical occurrence did not occur (social and/or convenience admission to a hospital).
- Anticipated day-to-day fluctuations of pre-existing disease(s) or condition(s) present or detected at the start of the study that do not worsen.

9.3.3. Definition of SAE

An SAE is defined as any serious adverse event that, at any dose:

1. Results in death

2. Is life-threatening

The term 'life-threatening' in the definition of 'serious' refers to an event in which the participant was at risk of death at the time of the event. It does not refer to an event, which hypothetically might have caused death, if it were more severe.

3. Requires inpatient hospitalization or prolongation of existing hospitalization

- In general, hospitalization signifies that the participant has been admitted (usually involving at least an overnight stay) at the hospital or emergency ward for observation and/or treatment that would not have been appropriate in the physician's office or outpatient setting. Complications that occur during hospitalization are AEs. If a complication prolongs hospitalization or fulfills any other serious criteria, the event is serious. When in doubt as to whether "hospitalization" occurred or was necessary, the AE should be considered serious.
- Hospitalization for elective treatment of a pre-existing condition that did not worsen from baseline is not considered an AE.

An SAE is defined as any serious adverse event that, at any dose:

- 4. Results in persistent or significant disability/incapacity
- The term disability means a substantial disruption of a person's ability to conduct normal life functions.
- This definition is not intended to include experiences of relatively minor medical significance such as uncomplicated headache, nausea, vomiting, diarrhea, influenza, and accidental trauma (e.g., sprained ankle) which may interfere with or prevent everyday life functions but do not constitute a substantial disruption.

5. Is a congenital anomaly/birth defect

6. Is a suspected transmission of any infectious agent via a medicinal product

7. Other situations:

• Medical or scientific judgment should be exercised by the investigator in deciding whether SAE reporting is appropriate in other situations such as significant medical events that may jeopardize the participant or may require medical or surgical intervention to prevent one of the other outcomes listed in the above definition. These events should usually be considered serious.

• Examples of such events include invasive or malignant cancers, intensive treatment for allergic bronchospasm, blood dyscrasias, convulsions or development of intervention dependency or intervention abuse.

9.3.4. Recording of TEAE, MAAE and/or SAE

AE and SAE Recording

• When a TEAE/MAAE/SAE occurs, it is the responsibility of the investigator to review all documentation (e.g., hospital progress notes, laboratory reports, and diagnostics reports) related to the event.

• The investigator will then record all relevant TEAE/MAAE/SAE information.

• It is **not** acceptable for the investigator to send photocopies of the participant's medical records to the Sponsor in lieu of completion of the Sponsor required form.

• There may be instances when copies of medical records for certain cases are requested by the Sponsor. In this case, all participant identifiers, with the exception of the participant number, will be redacted on the copies of the medical records before submission to the Sponsor.

• The investigator will attempt to establish a diagnosis of the event based on signs, symptoms, and/or other clinical information. Whenever possible, the diagnosis (not the individual signs/symptoms) will be documented as the AE/SAE.

9.3.4.1. Grading the Severity of TEAEs

Assessment of Severity

All TEAEs will be assessed by the investigator using a protocol-defined grading system. For events not included in the protocol-defined grading system, the following guidelines will be used to quantify severity:

Mild: events require minimal or no treatment and do not interfere with the participant's daily activities.

Moderate: events result in a low level of inconvenience or concern with the therapeutic measures. Moderate events may cause some interference with functioning.

Severe: events interrupt a participant's usual daily activity and may require systemic drug therapy or other treatment. Severe events are usually incapacitating.

Life threatening: any adverse drug experience that places the participant, in the view of the investigator, at immediate risk of death from the reaction as it occurred, i.e., it does not include a reaction that had it occurred in a more severe form, might have caused death.

Changes in the severity of an AE should be documented to allow an assessment of the duration of the event at each level of intensity to be performed. Adverse events characterized as intermittent require documentation of onset and duration of each episode.

9.3.4.1.1. Grading of Solicited Treatment-Emergent Adverse Events

Subjects should be instructed to rate solicited symptoms of reactogenicity that are collected within their Solicited Symptom Diary based on the severity scale presented in Table 9. Grading should be reviewed with the participant at each site occurring through 1 week post each vaccination (Day 1 - Week 1 and Week 4 - Week 5).

	Grading					
Symptom	Normal 0	Mild Grade 1	Moderate Grade 2	Severe Grade 3	Life Threatening Grade 4	
Fever (oral temp)	<100.4°F (<38.0°C)	100.4 – 101.1°F (38.0 – 38.4°C)	101.2 – 102.0°F (38.5 – 38.9°C)	102.1 – 104°F (39.0 – 40°C)	> 104.0°F (>40°C)	
Headache None No interference with activity Easily tolerated, causing minimal discomfort and does not interfere with everyday activities ^a		Repeated use of nonnarcotic pain reliever > 24 hours or some interference with activity	Significant; any use of narcotic pain reliever or prevents daily activity	ER visit or hospitalization		
		causing minimal discomfort and does not interfere with	Sufficiently discomforting to interfere with everyday activities	Prevents normal everyday activities or requires medical advice	ER visit or hospitalization	
Abdominal Pain	None	No interference with activity	Some interference with activity not requiring medical intervention	Prevents daily activity and requires medical intervention	ER visit or hospitalization	
Anorexia	None	No interference with activity	Some interference with activity not requiring medical intervention	Prevents daily activity and requires medical intervention	ER visit or hospitalization	
Nausea/ Vomiting	None	No interference with activity or 1 to 2 episodes/24 hours	Some interference with activity or >2 episodes/24 hours	Prevents daily activity, requires outpatient IV hydration	ER visit or hospitalization for hypotensive shock	
Diarrhea	None	2 to 3 loose stools or < 400 gms/24 hours	4–5 stools or 400 to 800 gms/24 hours	6 or more watery stools or > 800gms/24 hours or requires outpatient IV hydration	ER visit or hospitalization	
Malaise/ Fatigue	None	No interference with activity	Some interference with activity	Significant; prevents daily activity	ER visit or hospitalization	

Table 9 Grading of Solicited Symptoms of Reactogenicity

^a Everyday activities include attendance at work, school and usual habits of the participants.

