2.3.1. Risk Assessment

Vaxart.	, Inc.
---------	--------

Potential Risk of	Summary of Data/Rationale for Risk	Mitigation Strategy
Clinical Significance	Summary of Data/NationalC 101 NISK	mugation strategy
	antibodies to non-neutralizing S protein epitopes can enhance coronavirus infection (antibody- dependent enhancement, ADE). In macaques, an inactivated injected vaccine has produced some evidence of ADE, and in hamsters, an S protein-based vaccine also produced ADE (Kam, 2007; Wang, 2016).	assessed using case definition (Section 7.1.1).
Potential for vaccine related hypersensitivity, including anaphylaxis	Similar to other drugs, vaccines have the potential to cause allergic reactions. Vaccine components including immunizing antigens, adjuvants, culture derived proteins (e.g. gelatin) and other agents may have the potential to cause complications.	Monitor participants for any allergic reactions and onset of new illness during the trial duration.
Potential for systemic and gastrointestinal events (fever, headache, myalgia, abdominal pain, anorexia, nausea, vomiting, vomiting, diarrhea, and malaise/fatigue) following vaccination.	These systemic events are common adverse reactions seen with other vaccines, as noted in the Food and Drug Administration (FDA) Center for Biologics Evaluation and Research (CBER) guidelines on toxicity grading scales for healthy adult volunteers enrolled in preventive vaccine clinical studies. Given the route of delivery and mechanism of action for an ingestible vaccine some additional gastrointestinal (GI) events may also be observed.	Actively monitor systemic and GI-associated reactions (solicited symptoms) for 7 days following each study drug administration.

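### Abdominal pain or anorexia that prevents daily activity without medical intervention falls between Grades 2 and 3 in Table 9, so it may not count toward the Part 2 halting rule or the Dose 2 bar

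*Combined protocol and SAP*

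**What the plan says.** Participants rate solicited symptoms in a diary using Table 9 of Section 9.3.4.1.1, and "Grading should be reviewed with the participant at each site" through one week after each vaccination. Abdominal pain and anorexia have identical wording:

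- Grade 2: "Some interference with activity not requiring medical intervention"
- Grade 3: "Prevents daily activity and requires medical intervention"
- Grade 4: an emergency room visit or hospitalization

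Other rows set Grade 3 differently. Headache is "Significant; any use of narcotic pain reliever or prevents daily activity" and malaise/fatigue is "Significant; prevents daily activity". Myalgia is Grade 3 if it either stops normal activities or calls for medical advice.

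Section 9.3.4.1 has a general scale on which a severe event interrupts the participant's "usual daily activity and may require systemic drug therapy or other treatment". Its scope is limited: "For events not included in the protocol-defined grading system, the following guidelines will be used to quantify severity".

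The grade is used in three places:

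- **Halting.** Section 6.1.2, rule 2, halts Part 2 when five or more participants have the same or a similar solicited event of Grade 3 or higher, each vaccination assessed separately. Section 8.5.2 applies the rules to events in the vaccine group.
- **Dosing.** Section 4.2.2 withholds Dose 2 after any Grade 3 or 4 event that is judged related or lacks a plausible alternative explanation.
- **Endpoint.** Section 4.1 makes severity of solicited symptoms part of a Part 2 primary safety endpoint.

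**The concern.** Pain or loss of appetite that stops someone's day but is waited out at home is an ordinary presentation, and Table 9 has no cell for it. One site may apply the Grade 3 wording strictly and record Grade 2. Another may see that the event goes beyond some interference, look at the neighboring rows or the general definition of severe, and record Grade 3. The table has no tie-break and does not define medical intervention.

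These symptoms matter for this product. Section 2.3.1 says that with "an ingestible vaccine some additional gastrointestinal (GI) events may also be observed". Part 2 plans 30 to 60 sites in the U.S., Latin America, South Africa and/or India, so a shared reading cannot be assumed. Events that prevent daily activity could be left out of the halting count and the Dose 2 check, and the reported severity distribution could depend partly on site habit.

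**Working it through.** The documents state no figure for this point, so there is none to reproduce. The check compares the table cells and then traces the consequences.

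**1. Same impact, different rows.** Take a symptom that prevents daily activity and needs no medical intervention, narcotic or medical advice.

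| Row | Grade 3 condition | Result |
|---|---|---|
| Headache | narcotic use, or prevented activity | Grade 3 |
| Myalgia | prevented activity, or medical advice | Grade 3 |
| Malaise/fatigue | prevented activity | Grade 3 |
| Abdominal pain | prevented activity and medical intervention | not met |
| Anorexia | prevented activity and medical intervention | not met |

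**2. Does Grade 2 fit?** Only in part. The absence of intervention matches, but the impact does not. Headache and malaise/fatigue put some interference at Grade 2 and prevented activity at Grade 3, so the table treats these as different levels.

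**3. Does the general scale settle it?** It would call the event severe, since treatment there is optional. But it covers only events outside the protocol's own grading system, and Table 9 lists both symptoms.

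**4. A related cell.** Grade 3 nausea/vomiting lists prevented activity and outpatient IV hydration separated only by a comma, so it is unclear whether both are needed. In the diarrhea row, outpatient IV hydration is sufficient by itself.

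**5. Effect on the halting count.** The threshold as a share of planned vaccine recipients (Table 2) is 5 / 400 = 1.25%.

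Let k be the number of such events recorded as Grade 3 after a given vaccination, and q the number of other participants with a same or similar event of Grade 3 or higher. The rule is met when k + q ≥ 5.

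- Five affected vaccine recipients, q = 0: the count is 0 if all are recorded as Grade 2 and 5 if all are recorded as Grade 3. One recorded as Grade 2 gives 4, and the rule is not met.
- Five affected, q = 1: four recorded as Grade 3 are enough, since 4 + 1 = 5.
- Five participants with malaise/fatigue of the same impact: the count is 5 and the rule is met.

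**6. Effect on Dose 2.** One event decides it. Recorded as Grade 3 and judged related or unexplained, it bars the second dose. Recorded as Grade 2, it does not trigger that criterion.

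**7. What earlier data can say.** Section 2.1 reports only mild to moderate solicited symptoms in 35 recipients of the earlier, similar vaccine. Treating that as 0 severe events in 35, the one-sided 95% upper bound is 1 − 0.05^(1/35) = 0.082, about 8%. This is well above 1.25%, so those data do not exclude a rate at which the threshold matters. Those doses reached 5×10¹⁰ IU, below the 1×10¹¹ IU high dose here.

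**The case against.** The strongest reply is that the text is strict, not ambiguous. Grade 3 joins two conditions with *and*, the general scale is excluded by its own terms, and so Grade 3 is not met. On that view the complaint is a preference for a lower threshold. The first part stands: the strict reading is the better literal one. It does not rescue the table. The Grade 2 wording still does not describe the event, and under the strict reading gastrointestinal symptoms of an oral vaccine are graded lower than fatigue of equal impact.

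The second reply is that grade is not the only control, and this stands too. Section 6.2 lists an adverse event and physician decision as reasons to stop study drug. Section 8.5.1 lets the Medical Monitor request an IDMC review that can suspend the study, and requires events that might contribute to a halting rule to be flagged. Section 5.4.3 provides periodic unblinded IDMC review, and Section 8.5.2 provides ad hoc meetings. A cluster could well be noticed. None of these assigns the grade.

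Third, the diary and the IDMC Charter were not available. If the diary already has a rule for this case, Table 9 need only be aligned with it.

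The opening sentence of Section 6.1 could be read as ending the halting rules before Part 2. Section 4.2.2 applies Section 6.1.2 at any time during the study, and the Dose 2 bar does not depend on that sentence.

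**Conclusion.** The gap is real and should be corrected before Part 2. Abdominal pain or anorexia that prevents daily activity without medical intervention has no clear grade, or under the strict reading a lower grade than headache, myalgia or fatigue of equal impact. Such events may therefore not count toward halting rule 2 or the Dose 2 bar, and recorded severity can vary by site. The Part 1 rule, at two participants, has the same gap, but the Amendment 4 summary suggests that Part 1 has largely been conducted.

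A reader might infer more than the documents support:

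- *That the halting rule is likely to fail.* No rate of such events is given, so any probability would rest on an invented rate.
- *That every one of five such events must be Grade 3 for the rule to be met.* Other same or similar Grade 3 events also count, as step 5 shows.
- *That a Grade 2 record forces a second dose.* Investigators may stop dosing on other grounds.
- *That the efficacy result is in danger.* A missed Dose 2 removes a participant from the evaluable efficacy population, which is primary, but Section 8.3.2 also plans analyses in the all-available population, which needs only one dose.
- *That the arms are graded differently.* Part 2 is blinded with central 1:1 randomization, and nothing suggests bias between arms.

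**What to change.** Before Part 2:

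1. In the abdominal pain and anorexia rows, set Grade 3 to *Prevents daily activity, whether or not medical intervention is required*.
2. In the nausea/vomiting row, set Grade 3 to *Prevents daily activity or requires outpatient IV hydration*.
3. State that the highest grade met applies, so an emergency room visit or hospitalization in the abdominal pain and anorexia rows stays Grade 4.
4. Align the diary text.

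For abdominal pain and anorexia, every clearly graded case keeps its grade: no interference is 1, some interference without intervention is 2, prevented activity with intervention is 3, and an emergency room visit or hospitalization is 4. Only prevented activity without intervention changes, from unset to 3.

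The fix should not make some interference plus professional care a Grade 3 event. That case also fits no cell today, but grading it as 3 would be a new threshold and could bar Dose 2 after treatment of moderate pain. If the sponsor wants to settle it, that is a separate decision.

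The cost is three cells, one sentence and the diary text. There may be slightly more Grade 3 events, and with them a few more pauses for IDMC review or Dose 2 exclusions. Each exclusion takes one participant from the evaluable efficacy population, against a total dropout allowance of 400 − 341 = 59 per arm. Grades for the changed rows will have limited comparability with Part 1.
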